The evolving understanding of pain physiology in children has led to advancements in multimodal analgesic techniques. Pain management plans encompass a spectrum of interventions ranging from medications, psychological support, and regional anaesthesia. Caudal anaesthesia is one of the most commonly performed regional anaesthesia techniques in paediatrics. A single dose of bupivacaine in the epidural space when accessed through the sacral hiatus provides analgesia for

almost the entirety of the surgical procedure time, but unfortunately, its action is time limited in the postoperative period. ⁽⁸⁾

An ultrasound guided technique has been proven to provide better accuracy and success rate along with decreased puncture rates and increased first puncture success rates compared to a blind caudal block. Transverse and longitudinal views using ultrasound illustrate the sacrococcygeal ligament, the two sacral cornua and the dura mater with epidural space. ^(9, 10)

Erector spinae block is a relatively new technique first described by Forero et al in 2016. Since then, it has been described as an effective block in the paediatric population. It effectively blocks somatic and visceral pain when administered correctly in thoracic or abdominal surgeries, unilaterally or bilaterally. ^(11, 12)

Its analgesic effect appears to be due to injecting local anaesthetic into the interfacial plane between the transversus process and erector spinae accompanied by diffusion into paravertebral and intercostal spaces, where it affects the ventral and dorsal rami of spinal nerves. ^(13, 14)

As the field continues to progress, ongoing research and clinical innovations aim to provide an effective approach to the well-being of young surgical recipients with the most amount of pain control. In this study, we hypothesize that, erector spinae block may be an alternative technique for caudal block for perioperative analgesia in children undergoing lower abdominal surgeries. Our aim will be to compare between erector spinae block and the caudal block to determine which one will provide better postoperative analgesia for a longer duration with fewer side effects.

AIM OF THE WORK

Primary aim: is to evaluate the efficacy of postoperative pain management using the Face, Legs, Activity, Cry, Conceal ability (FLACC) Pain Scale.

Secondary aim:

- Intraoperative haemodynamic changes.
- The time to first rescue analgesic.
- Total postoperative analgesic requirements.

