- Parent satisfaction with a 5-point Likert scale questionnaire. ⁽¹⁵⁾
- Number of patients required rescue analgesic postoperatively.
- Time to Modified Aldrete score ≥ 9 . ⁽¹⁶⁾
- PACU stay (min).
- Incidence of any adverse effects.

PATIENTS

After approval of the Medical Ethics Committee of the Faculty of Medicine, Alexandria University. An informed written consent from every patient from parent/caregiver will be done in this study, the current study will be performed in El Shatby University Hospital for children on 60 patients who will be scheduled for elective lower abdominal surgeries under general anaesthesia.

The minimum total hypothesized sample size of 60 eligible study participants will be needed to evaluate the efficacy of postoperative pain management using the Face, Legs, Activity, Cry, Consolability (FLACC) Pain Scale. Taking into consideration an effect size of 20%, significance level of 5% and power of 8-% using Chi Square Test.

This study will be a prospective randomized study. Randomization was done using a computer-generated random numbering of each study patient where even numbers will be group (ESB) and odd numbers will be group (CB). Opaque sealed envelopes will be used and will be opened in the operative theatre by an investigator who will be blinded to the study groups. The parents, children, surgeon, and the investigators who will collect the data after the block will be blinded to the study group. Patients will be randomized into two equal groups:

Group (ESPB): patients will receive bilateral ultrasound guided erector spinae block of dilute solution at dose 0.4 ml/kg of 0.25% bupivacaine between the 10th transversus process and erector spinae muscle on each side, provided that it does not exceed toxic dose of bupivacaine 2.5 mg/kg. ⁽¹⁷⁾

Group (CB): patients will receive ultrasound guided caudal epidural block of dilute solution bupivacaine 0.25% at dose 1ml/kg, provided that it does not exceed toxic dose of bupivacaine 2.5 mg/kg. ⁽¹⁸⁾

Inclusion criteria:

- Age between 2-7 years old.
- ASA I-II.
- Elective surgery under general anaesthesia.
- Lower abdominal surgery.

Exclusion criteria:

- Parent/caregiver refusal.
- Allergy to one of the study medications.
- Renal or cardiac disease.
- Infection or redness at the site of injection.
- Clinically significant coagulopathy.
- Spinal anomalies.
- Altered mental status.
- Developmental delay.
- Additional surgery at different surgical sites.
- Block failure.

METHODS

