Preoperative evaluation

1. All patients will be evaluated the day before surgery through proper history taking and clinical examination to exclude cardiovascular, respiratory, neurological, and metabolic diseases.
2. Routine laboratory investigations including:
 - Complete blood count (CBC).
 - Bleeding time.
 - Clotting time.
 - Prothrombin activity & INR.
 - Random blood sugar.
3. All parents will be informed about the techniques of both erector spinae and caudal blocks, and a written consent will be obtained from every parent.
4. All children will not take any solid food for 6 hours preoperatively, but each will be allowed to drink clear fluids up to 2 hours before induction of anaesthesia.

Anaesthetic Technique:

- On arrival to operating theatre, all patients will be attached to a multichannel monitor to display continuous ECG monitoring, non-invasive BP monitoring and peripheral oxygen saturation (SpO₂), nasopharyngeal temperature monitor using Draeger Monitor model Vista 120, Germany.

- Inhalational induction will be conducted using incremental concentrations of sevoflurane up to 8% with 100% O₂ (4 L/min) via face mask (Jackson-Rees modification of Ayer's T-piece).
- After loss of consciousness, a 24G cannula will be inserted into a peripheral vein.
- Laryngeal mask airway (LMA) that is appropriate size to age will be inserted, and anaesthesia will be maintained with oxygen and Isoflurane at double MAC delivered via Jackson-Rees circuit with pressure supported spontaneous ventilation (Trigger Sensitivity 0.7 L/min, PEEP 3, PS 10) using Penlon Ventilator (AV-S Model, Made in UK).
- A diclofenac sodium suppository will be administrated in a dose of 1 mg/kg.
- Bolus intravenous lactated ringers' will be given at the dose of 10 ml/kg.
- No intraoperative muscle relaxants, sedatives, or IV opioids will be administered.

Block Procedure:

All blocks will be given under ultrasound guidance (Philips ClearVue 350 made in USA) using a longitudinal parasagittal transducer probe (6–12 MHz) by the same experienced anaesthesiologist who will not participate in data collection, another anaesthetist will be called to the operating room after preparing the patient and block procedure so that, he will be blinded to group allocation.

Group ESPB:

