Patients will be placed in lateral decubitus position. The area at the level of and 1-2 cm lateral to T10 over both sides of spine will be sterilized with 10% povidone-iodine and the probe will be placed in sterile gloves. After visualization of the erector spinae

muscle, the needle will be inserted proximally. After hydro dissection, the needle tip will be confirmed to be between the fascia of the erector spinae muscle group and the transverse process, the dilute solution of bupivacaine 0.25% at dose 0.4 ml/kg will be injected on each side.⁽¹⁶⁾ After the block patients will be placed in supine position and surgery will take place 10 minutes after injection.

Group CB:

After induction of general anaesthesia, the patient will be placed in left lateral decubitus position with the upper hip flexed at 90-degree angle. The needle insertion site will be sterilized using 10% povidone-iodine and the probe will be covered with sterile gloves. The sacral hiatus will be visualized using the ultrasound as two hyperechoic band like lines, the superior line being the sacrococcygeal ligament and the inferior line the dorsum of the pelvic surface of the sacrum. A “pop” or “give” is usually felt when the sacrococcygeal ligament is penetrated. A 22G needle will be introduced at a 45° angle. Cautious aspiration will be performed to rule out an inadvertent systemic or spinal needle location then patients will receive dilute solution of bupivacaine 0.25% at dose 1 ml/kg between the two sacral cornua while observing caudal epidural space dilation or turbulent flow with Doppler. Then, we will wait 10 minutes before the first surgical incision.⁽¹⁸⁾

Haemodynamic will be closely monitored. Failure of block will be defined as increase in heart rate and or mean arterial blood pressure (MAP) above 10% than baseline values at the beginning of surgery, intravenous fentanyl will be given at dose 0.5 ug/kg and patient will be excluded from the study and replaced by another patient. Methods to keep normothermia will be done via warmed iv fluids and forced air-warming blankets.

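### Children whose allocated block fails are excluded and replaced after randomisation, so postoperative outcomes are compared only among children whose block passed the success rule

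*Protocol*

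**What the plan says.** The order of events is set out in two places in the Protocol.

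- **Allocation (PATIENTS, randomisation).** "Opaque sealed envelopes will be used and will be opened in the operative theatre by an investigator". The allocated block follows, and surgery starts 10 minutes after the injection in both groups (METHODS, Block Procedure).
- **Failure rule (METHODS, end of Block Procedure).** Failure is a rise in "heart rate and or mean arterial blood pressure (MAP) above 10% than baseline values at the beginning of surgery". Fentanyl is then given and the "patient will be excluded from the study and replaced by another patient".
- **Exclusion criteria (PATIENTS).** "Block failure" appears in the same list as parental refusal and coagulopathy, although it cannot be known before allocation.
- **Aim (introduction).** The comparison is meant "to determine which one will provide better postoperative analgesia for a longer duration with fewer side effects".
- **Outcomes (MEASUREMENTS).** FLACC is scored at 15 and 30 minutes and then two-hourly over 8 hours. Time to first analgesic, total analgesics, rescue use and parent satisfaction also come after the point of exclusion.

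No section provides for follow-up of an excluded child or says how the replacement is allocated. Only the Protocol is available; a statistical analysis plan may exist.

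**The concern.** Block failure is a result of the randomised treatment, not an eligibility condition. Removing children because of it means that the two groups compared after surgery are no longer the two groups that were randomised. If one block fails more often, or fails in a different kind of child, that disadvantage drops out of the comparison. This bears directly on the question of which block gives better postoperative analgesia.

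This cannot be left to an analysis plan. Such a plan can define analysis sets, but it cannot analyse FLACC scores that were not recorded because the child had left the study.

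Two related weaknesses come from the same rule:

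- It selects on heart rate and MAP at the start of surgery, while intraoperative haemodynamic change is a secondary aim, so the selection may carry over to later, correlated readings. The rule's baseline is also undefined: MEASUREMENTS item 2 lists three readings before surgery (before induction, after induction, after the block).
- MEASUREMENTS item 10 names failed block as a complication of the erector spinae technique but not of the caudal technique. Children who fail at the start of surgery have by then left the study in both arms. A later failure in a retained erector spinae child could still be recorded, so failure would not be counted on the same footing in the two arms.

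**Working it through.** **Plan's own figures.** The Protocol gives no failure rate and no rescue rate, so there is no figure on this point to reproduce. The one number used from it is the total of 60, that is 30 per arm. How 60 was derived is a separate matter and nothing below depends on it. Every rate below is an assumption.

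**Formula.** For one arm let f be the failure rate, r the share needing rescue after a failed block, and p the share needing rescue after a successful block.

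- All randomised children: f·r + (1 − f)·p = p + f(r − p)
- Successful blocks only: p
- Difference hidden by the exclusion (all-randomised contrast minus success-only contrast): f1(r1 − p1) − f2(r2 − p2)

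**Unequal failure, 20% against 5%, p = 0.40 in both arms.** The success-only comparison shows 0 in every row.

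| r (both arms) | Arm 1: 0.40 + 0.20(r − 0.40) | Arm 2: 0.40 + 0.05(r − 0.40) | Hidden difference |
|---|---|---|---|
| 0.30 | 0.380 | 0.395 | −1.5 points |
| 0.40 | 0.400 | 0.400 | 0 |
| 0.60 | 0.440 | 0.410 | 3.0 points |
| 0.70 | 0.460 | 0.415 | 4.5 points |
| 1.00 | 0.520 | 0.430 | 9.0 points |

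**Milder contrast, 10% against 5%, same p.** (0.10 − 0.05)(r − 0.40) gives 1.0, 1.5 and 3.0 points for r = 0.60, 0.70 and 1.00.

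**Equal failure of 15%, but different consequences of failure.** With r − p of 0.60 in one arm and 0.20 in the other: 0.15 × 0.60 − 0.15 × 0.20 = 0.06, or 6 points. Equal failure rates alone do not remove the bias.

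**Outer limits, f from 5% to 20%, each quantity free to vary by arm.**

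- r − p from −0.10 to 0.30: at most 0.20 × 0.30 + 0.20 × 0.10 = 0.08, so −8 to +8 points.
- r − p from −0.10 to 0.60: at most 0.20 × 0.60 + 0.20 × 0.10 = 0.14, so −14 to +14 points.

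These limits are corners: they need failure to raise rescue in one arm and lower it in the other.

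**Scale.** The sample size statement reads "Taking into consideration an effect size of 20%, significance level of 5" per cent. If that effect size means 20 percentage points, which the Protocol does not say, then 3 to 9 points is 3/20 = 15% to 9/20 = 45% of it. The −1.5 and 0 rows belong to the same range.

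**Data lost.** With the same failure rate in both arms, the expected number of the first 60 randomised children without postoperative data is 60 × 0.05 = 3, 60 × 0.10 = 6, 60 × 0.15 = 9 or 60 × 0.20 = 12. At 5% failure the chance of losing at least one is 1 − 0.95^60 = 0.954.

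**The case against.** **Working blocks are a fair question.** The rule is stated in advance, applies to both arms alike, and agrees between the exclusion criteria and the methods. An interest in duration of analgesia can be read as a question about working blocks. That comparison is legitimate, but as a secondary one. As written it is the only one with observed postoperative data behind it.

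**An analysis plan could help in part.** If failures are counted by arm, each could be scored as a treatment failure, or best- and worst-case bounds could be put on rescue use. This would narrow the problem for rescue. Observed FLACC scores, the primary outcome, would still be missing.

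**The size is assumed.** This stands. The sign is unknown, the milder contrast hides only 1 to 3 points, and the standard error of a rescue difference at 40% with 30 per arm is √(2 × 0.40 × 0.60 / 30) = 0.126, about 12.6 points. All the figures concern rescue use; none is available for FLACC, although a score of 4 or more is what triggers rescue. The illustrations show that the effect can range from nothing to several points, and the case does not rest on them.

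**Blinding.** Data collectors after the block are blinded, and "another anaesthetist will be called to the operating room after preparing the patient and block procedure". This limits uneven judgement of failure if one of these people makes it, which the Protocol does not say. It does nothing about a real difference in failure between the blocks.

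**Side points.** The undefined baseline would remain a gap even if all children were followed. The uneven complication lists are an asymmetry more than a flat contradiction. Neither changes the main point.

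**Conclusion.** The concern holds and should be corrected before data are collected. The Protocol excludes and replaces children on a response to their allocated block and makes no provision to follow them, so the randomised comparison of postoperative outcomes is lost at that step.

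Confidence is high on the structure, which rests on the Protocol's own wording, and low on the size and direction of bias, which cannot be derived from it. Bias can be expected to be small only if both the failure rates and the kinds of children who fail are similar in the two arms, or if the terms happen to cancel. The Protocol supports neither, and the design prevents checking. Under the assumed rates the hidden difference in rescue use runs from slightly negative through zero to about 9 points, with wider limits only in extreme combinations. The importance of the point rests on the irrecoverable loss of primary-outcome data after allocation.

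**What to change.** 1. Delete "Block failure" from the exclusion criteria, and delete the rule that the "patient will be excluded from the study and replaced by another patient". This also removes the open question of how replacements are allocated.
2. State that every randomised child is followed to 8 hours, with FLACC and rescue recorded, whatever the result of the block, and that the primary comparison analyses each child in the allocated group.
3. Record block failure as an outcome in both arms, bring the two complication lists into line with this, and state which recorded reading is the baseline for the 10% rule and who judges failure.
4. Give the comparison among successful blocks as a sensitivity analysis.
5. Leave the management of the individual child unchanged. Because failed-block children would now stay in the study, reconcile the sentence "No intraoperative muscle relaxants, sedatives, or IV opioids will be administered" with the fentanyl given at block failure; at present the two read as a rule with an exception.

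**Cost.** Protocol wording, plus the already planned 8-hour follow-up in about 3 to 12 of 60 children at an assumed 5% to 20% failure. The primary estimate would then include some children given intraoperative fentanyl, so it describes the result of allocating each block together with what follows its failure, and early FLACC should be read in that light. The sensitivity analysis would have fewer children: at an assumed 20% against 5% failure, 30 × 0.80 = 24 and 30 × 0.95 = 28.5 per arm.

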At the end of surgery, O₂ 100% > 5 L/min will be continued after the discontinuation of sevoflurane. Once the patient shows adequate recovery from anaesthesia, oropharyngeal suction will be performed, and the LMA will be removed. Patients will be transferred to the post anaesthesia care unit (PACU) for monitoring of vital signs. Children will be considered ready for discharge from the PACU when being fully awake, stable vital signs for 30 min, no pain, no nausea or vomiting and the Modified Aldrete post-anesthesia score was ≥ 9 .

MEASUREMENTS

The following parameters will be measured:

1. Demographic data:

- Age.
- Sex.
- Weight.
- **Duration of surgery:** (time from the start of induction till discontinuation of the inhaled anaesthetics in minutes).
- **Duration of anaesthesia:** (from skin incision to final skin sutures in minutes).
- **Type of surgical procedure.**

2. Haemodynamic measurements:

- Heart rate (beats/min) using lead II electrocardiogram (ECG) waves.
- Mean arterial blood pressure: (MABP) in mmHg.
- Oxygen saturation.

They will be monitored and recorded at the following times:

- Pre-induction.
- Post-induction.
- Immediately after performing the block.
- At the start of surgical manipulation.
- Intraoperative every 10 minutes.
- At the end of the operation.

3. Time to Modified Aldrete score ≥ 9 .
4. PACU stay (min).
5. Postoperative pain: It will be assessed 15, 30 minutes in recovery room then every 2 hours the next 8 hours using FLACC Behavioural Pain Assessment Scale. Postoperative pain score will be assessed by a nurse blinded to the patient's anaesthetic management.⁽¹⁹⁾

FLACC Behavioural Pain Assessment Scale 5 parameters: Table (1)

1. Face.
2. Legs.
3. Activity.
4. Cry.
5. Consolability.

Table (1): FLACC Behavioural Pain Assessment Scale

Category	0 score	1 score	2 score
Face	No Particular expression or smile	Occasional grimace or frown; withdrawn, disinterested	Frequent to constant frown, clenched jaw, quivering chin
Legs	Normal position or relaxed	Uneasy, restless, tense	Kicking or legs drawn up
Activity	Lying quietly, normal position, moves easily	Squirming, shifting back and forth, tense	Arched, rigid, or jerking
Cry	No cry (awake or asleep)	Moans or whimpers, occasional complaint	Crying steadily, screams or sobs; frequent complaints
Consolability	Content, relaxed	Reassured by occasional touching, hugging, or being talked to; distractible	Difficult to console or comfort

Interpreting the Behavioural Score: Table (2)

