Each category is scored on the 0–2 scale, which results in a total score of 0–10.

Table (2): Interpreting the FLACC Behavioural Score

0	Relaxed and comfortable
1–3	Mild Pain
4–6	Moderate pain
7–10	Severe Pain

6. Time to first postoperative analgesic request

The time elapsed between end of surgery and first administration of an analgesic.

A postoperative pain score of ≥ 4 will be managed with paracetamol 10 mg/kg intravenous then will be repeated every 6 hours as required.

If pain persists after dose of paracetamol or score >4 , nalbuphine will be given at dose 0.1 mg/kg intravenously.

7. Total postoperative analgesics requirement will be recorded.

8. Number of patients who will require postoperative rescue analgesia.

9. Parent satisfaction:

Parent satisfaction with a 5-point Likert scale questionnaire.

10. Side effects:

A) Side effects related to bupivacaine:

- **CNS:** Nausea, vomiting, circumoral numbness, facial tingling, vertigo, tinnitus, restlessness, anxiety, dizziness, seizure, coma.
- **Cardiovascular:** hypotension, arrhythmia, bradycardia, heart block, cardiac arrest.
- **Allergic reactions**

B) Side effects related to the erector spinae technique:

In addition to the common complications associated with any peripheral nerve block (local anaesthetic toxicity, intravascular injection, nerve injury, bleeding, and infection), vascular puncture, pleural puncture, pneumothorax, and failed block are the primary complications.

C) Side effects related to the caudal block technique:

Epidural abscess, meningitis, post dural puncture headache, subdural injection, pneumocephalus, air embolism and back pain.

ETHICS OF RESEARCH

Research on human or human products:

- Prospective study: Informed consent will be taken from patients. In case of incompetent patients, the informed consent will be taken from the guardians.
- Retrospective study: Confidentiality of records will be considered.
- DNA / genomic material: Informed consent for DNA / genomic test and for research will be taken from patients. No further tests will be carried out except with further approval of committee and patients. If the samples will travel outside Egypt the researcher will be responsible for transportation and security approval.
- All drugs used in the research are approved by the Egyptian Ministry of Health.

Research on animal:

- The animal species are appropriate for the test.
- After test, if the animal will suffer, it will be euthanized and properly disposed.

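### FLACC scores leg behaviour and only the caudal arm is injected in the sacral epidural space, yet no leg-movement record is planned, so a motor effect on the pain score could not be told from less pain

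*Protocol*

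**What the plan says.** - **Primary outcome.** Under AIM OF THE WORK, the primary aim "is to evaluate the efficacy of postoperative pain management using the Face, Legs, Activity, Cry" and consolability scale.
- **Scoring.** MEASUREMENTS, item 5: "Each category is scored on the 0–2 scale, which results in a total score of 0–10". In Table (1), Legs runs from 0 for a relaxed or normal position, through 1 for unease or tension, to 2 for "Kicking or legs drawn up". The zero category of Activity is "Lying quietly, normal position, moves easily".
- **Reading times.** A blinded nurse scores FLACC at 15 and 30 minutes in recovery and then two-hourly over eight hours, which makes six readings.
- **Caudal arm.** METHODS, Block Procedure, Group CB: "patients will receive dilute solution of bupivacaine 0.25% at dose 1 ml/kg between the two sacral cornua", with dilation of the caudal epidural space observed on ultrasound.
- **Erector spinae arm.** PATIENTS, Group (ESPB): the injection is "between the 10th transversus process and erector spinae muscle on each side". The introduction describes its action as "diffusion into paravertebral and intercostal spaces, where it affects the ventral and dorsal rami of spinal nerves". It mentions no lumbar or sacral spread.
- **Rescue.** MEASUREMENTS, item 6: a pain score of 4 or more leads to an analgesic.
- **Safety.** Fewer side effects is part of the aim stated at the end of the introduction. The secondary aims include adverse effects of any kind. Item 10 lists effects of bupivacaine (A), of the erector spinae technique (B) and of the caudal technique (C). List C reads "Epidural abscess, meningitis, post dural puncture headache, subdural injection, pneumocephalus, air embolism and back pain". None of the three names leg weakness or motor block, and no other measurement item records leg movement.

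**The concern.** A behavioural pain scale compares two groups fairly when pain is the main thing that changes the behaviour. Here one of the five items is scored from the legs, and the two techniques place the local anaesthetic at different levels relative to the nerve roots that supply the legs. If one technique reduces leg movement, its Legs score can fall without any difference in pain.

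Such an error would lie in one arm only, so randomisation does not balance it. Blinding the nurse does not help either, because the behaviour being scored is itself altered. It would also pass into time to first rescue, number of children rescued and total analgesic use, all of which depend on the FLACC total reaching 4. Because leg movement is not recorded, nobody could tell afterwards whether a lower caudal score reflected better analgesia. Leg weakness that was never recorded cannot be recovered by a later analysis plan.

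**Working it through.** The protocol states no figure for this effect, so there is none to reproduce. The check is a reading of the items followed by a sizing under stated assumptions.

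**1. Weight of the Legs item.** Five items scored 0–2 give 0–10, so Legs can move a child's total by at most 2 points.

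**2. The rescue threshold.** Take Face 1, Legs 1, Activity 1, Cry 1, Consolability 0: 1 + 1 + 1 + 1 + 0 = 4, which triggers rescue. If Legs falls to 0: 1 + 0 + 1 + 1 + 0 = 3, which does not. One point on one item can decide.

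**3. Possible shift in the caudal mean (assumed inputs).** Shift = share of caudal children affected × Legs points lost per affected child.
- Low: 0.2 × 0.5 = 0.10 points.
- High: 0.5 × 1 = 0.50 points.

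Neither the shares nor the points lost come from the protocol.

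**4. Chance of a false difference at one time point.** Inputs: 30 per arm (60 in two equal groups, PATIENTS), two-sided 5%, no true pain difference, SD assumed between 1.0 and 2.5 because the protocol gives none. The comparison of means is a convenient model, not an analysis stated in the protocol.

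SE = SD × √(2/30) = 0.258 × SD, and P = Φ(b/SE − 1.96) + Φ(−b/SE − 1.96), where b is the shift.

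| Shift b | SD 1.0 (SE 0.258) | SD 2.5 (SE 0.645) |
|---|---|---|
| 0 | 5% | 5% |
| 0.10 | b/SE 0.387: 6.7% | b/SE 0.155: 5.3% |
| 0.25 | b/SE 0.968: 16.2% | b/SE 0.387: 6.7% |
| 0.50 | b/SE 1.936: 49.1% | b/SE 0.775: 12.1% |

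**5. Effect on the share reaching 4 (illustrative).** Each item is drawn as binomial(2, p), with p varying between children as a beta distribution with mean 0.3 and parameters summing to 3. The mean total is 3 and the SD 2.61. The share at or above 4 is 37.3%. Setting Legs to 0 in half the caudal children gives 33.1%, a fall of 4.2 percentage points, or 0.042 × 30 ≈ 1.3 children. Setting it to 0 in all of them gives 28.8%, or 0.085 × 30 ≈ 2.6 children. This removes the whole Legs score from each affected child, so it is an upper bound for the share assumed.

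**6. Is leg movement captured elsewhere?** Items 1–10 cover demographics, haemodynamics, time to a modified Aldrete score of at least 9, PACU stay, FLACC, three analgesic measures, parent satisfaction and side effects. The Aldrete outcome is a time to a total score, so it gives no leg reading at the FLACC times. Adverse effects of any kind could include leg weakness that someone reports, but no check for it is planned.

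**The case against.** The strongest reply is that the premise is not in the protocol. It does not say that caudal bupivacaine at this dose weakens the legs after surgery, how often, or for how long. That stands: the mechanism is inferred from the injection sites and general anatomy, so the point has to remain conditional. FLACC is also a standard, cited scale, and using it is not in itself an error.

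A reader might infer more than the documents support:
- **That a weak-legged child scores 0 on Legs whatever the pain.** Weak is not immobile, and the middle category can be met by tension or restlessness alone.
- **That Activity is biased the same way.** Its zero category is "Lying quietly, normal position, moves easily". A child with weak legs might not be judged to move easily and could score higher, so the direction is unclear.
- **That the bias is large.** The early readings, when the block is densest, are probably also when there is least pain and so least Legs score to lose. The 0.5-point case combines a high share affected with a high Legs score, which may seldom occur together. At 0.1 the effect is close to nil.
- **That the safety comparison cannot see leg weakness at all.** The open adverse-effect outcome could catch a spontaneous report.
- **That urinary retention belongs to the same problem.** It has no bearing on FLACC scoring.

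Two objections concern the remedy. A sensitivity analysis is often left to an analysis plan, and one may exist. That is fair for the analysis, but not for leg movement, which has to be collected under the protocol. The other is that a leg-movement tick could hint at the arm. Recording it after the score protects that reading but not the later ones. The added risk is small because the nurse already watches the legs to score FLACC.

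**Conclusion.** The concern holds in conditional form. The primary scale includes a leg item, only one arm is injected in the sacral epidural space, and the protocol collects nothing that would show whether leg weakness lowered the caudal scores. If it did, the Legs item would favour the caudal arm for a reason other than analgesia, mainly at the early readings, and rescue outcomes would follow.

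The size is unknown and may be negligible. Over the assumed shifts and SDs, the false-difference rate at one time point runs from about 5% to 49%. Those limits rest on the assumed share affected, Legs points lost and SD, not on trial data. The documents do not show that the trial is biased towards caudal block; they show that such a bias would go undetected. This is a worthwhile, inexpensive improvement rather than a defect that invalidates the design.

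**What to change.** 1. **Keep the item scores.** State in MEASUREMENTS, item 5, that the five FLACC items are stored separately. Report the total without Legs (0–8) by group as a prespecified sensitivity analysis beside the 0–10 total. The item scores are already taken at each reading, so this adds no assessment. The 0–8 score is unvalidated and should serve only as a sensitivity analysis. It cannot correct the rescue outcomes, which are triggered by the full score.
2. **Record leg movement in both groups.** After each FLACC score is written down, the assessor records whether the child moves both legs (yes/no). The cost is one tick-box at each of six readings and a small added risk of unblinding at later readings.
3. **Name leg weakness in item 10 for both groups,** so that it is looked for equally rather than left to spontaneous report. The cost is one line on the side-effect form.

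None of these changes alters treatment, the rescue rule or the sample size.
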